## **13 SITE MONITORING**

The study monitors are designated as agents of the Sponsor and are assigned to oversee the conduct and progress of the study and to be the principal communication link between the Sponsor and the Investigator.

The study monitors will be involved in Investigator selection and training, assurance of IRB approvals, and periodic on-site inspection and monitoring of sites and records, to ensure continued compliance with the protocol and adequacy of the Investigator and the facility to carry out the study. In addition, the monitor will verify that the device is being used in accordance with the protocol instructions.

The site may also be subject to a quality assurance audit by personnel of the Sponsor as well as by FDA representatives.

The monitor will perform several types of site visits during the course of the study. In all cases, the study monitor will provide a written summary of the visit, including necessary follow-up items, to the Investigator and Sponsor.

It is important that the Investigator(s) and the relevant site personnel are available during the monitoring visits, and possible audit, and that sufficient time is devoted to the process.

### **13.1 Study Initiation Visit**

Before the study begins, the study monitor will visit the site. The purpose of this visit is to review with the Investigator and staff the provisions and proper conduct of the clinical evaluation. This includes a detailed review of the protocol and eCRFs with instructions as to their completion, as well as reviewing regulations pertaining to the conduct of the clinical study. Arrangement for timely and accurate reporting of clinical data and relevant medical events will be established as well as ensuring safe and secure storage for the study devices.

The study monitor will:

- Confirm that the ICF to be used is the one approved by the IRB;
- Verify that all necessary documents are on file at the site; and
- Confirm that there are provisions to continue and maintain all documents and records throughout the study as required by GCP regulations.

### **13.2 Ongoing Monitoring Visits**

The study monitor will maintain personal contact with the Investigator and staff throughout the study by telephone, e-mail, fax, mail, and on-site visits. On-site monitoring will begin after the first subjects are enrolled and continue until the study is completed. The monitoring will assure continued protocol compliance, adequate subject enrollment, accurate data reporting (including the comparison of eCRFs with subject records), device accountability (if required), and continued IRB acceptance of the study. The study monitor will evaluate and summarize the results of each visit in written reports, identifying any ongoing data problems with any study site and specifying recommendations for resolution of noted deficiencies. A formal monitoring plan will describe the planned extent of source data verification.

### **13.3 Final Monitoring Visit**

At the completion of the study, the study monitor will conduct a final on-site visit. The purpose of this visit is to collect all outstanding study data documents, confirm that the Investigator's files are accurate and complete, review the record retention requirements with the Investigator, provide the return of unused devices (if required) to the sponsor, review records which account for device shipment (if required), and assure that all applicable requirements for closure of the study are met. The actions and observations made at this visit will be recorded and filed.

## **14 TERMINATION OF STUDY**

Sponsor reserves the right to suspend enrollment or terminate the study at any time as set forth in the Clinical Study Agreement. Written notice will be submitted to the Investigator in advance of such termination.

Sponsor may suspend enrollment or terminate the study at a specific site for reasons including, but not limited to, inadequate data collection, low subject enrollment rate, achievement of the total enrollment, or non-compliance with the protocol or other clinical research requirements.

## **15 REPORTING REQUIREMENTS**

The Investigator must promptly report to Sponsor any withdrawal of IRB approval at the site. Additional reporting requirements of the Investigator include:

- Reporting all ICF violations to the IRB
- Reporting all unanticipated problems, whether AEs or not
- Reporting all device-related AEs to Davol Field Assurance Department

As well as any additional requirements per the local IRB.

## **16 RECORD RETENTION**

The investigator shall retain all study records for a period of 2 years after the investigation is terminated or completed, or until the records are no longer required as determined by the Sponsor. The investigator may withdraw from the responsibility to maintain records for the period required and transfer custody of the records to any other person who will accept responsibility for retaining them with pre-approval. Notice of a transfer shall be given to the Sponsor not later than 10 working days after transfer occurs.

**Appendix 2: Phasix™ Mesh Instructions for Use**

---

**BAIRD**  
DAVOL INC.

## PRODUCT DESCRIPTION

PHASIX™ Mesh is a resorbable mesh prepared from poly-4-hydroxybutyrate (P4HB). P4HB is produced from a naturally occurring monomer and is processed into monofilament fibers and knitted into a surgical mesh.

PHASIX™ Mesh degrades through a process of hydrolysis and a hydrolytic enzymatic digestive process. It has been developed to minimize the variability of resorption rate (loss of mass) and strength and provide support throughout the expected period of healing.

Pre-clinical implantation studies indicate that the resorption of the PHASIX™ fibers is minimal throughout the 12 week expected period of healing and up to about 26 weeks post implantation. Resorption of the fibers is essentially complete in 12 to 18 months.

## INDICATIONS

PHASIX™ Mesh is indicated to reinforce soft tissue where weakness exists, such as the repair of hernia or other fascial defects that require the addition of a reinforcing or bridging material to obtain the desired surgical result.

## CONTRAINDICATIONS

Because PHASIX™ Mesh is fully resorbable, it should not be used in repairs where permanent wound or organ support from the mesh is required.

## WARNINGS

1. Device manufacture involves exposure to tetracycline hydrochloride and kanamycin sulfate. The safety and product use for patients with hypersensitivities to these antibiotics is unknown. Use of this device in patients with known allergies to tetracycline hydrochloride or kanamycin sulfate should be avoided.
2. The safety and effectiveness of PHASIX™ Mesh in neural tissue and in cardiovascular tissue has not been evaluated or established.
3. The safety and effectiveness of PHASIX™ Mesh in pediatric use has not been evaluated or established.
4. The placement of PHASIX™ Mesh in direct contact with bowel or viscera is not recommended.
5. If an infection develops, treat the infection aggressively. Consideration should be given regarding the removal of the mesh. An unresolved infection may require removal of the device.
6. This device is supplied sterile. Inspect the device and packaging prior to use to be sure they are intact and undamaged.
7. This device is for single use only. Do not resterilize or reuse any portion of the PHASIX™ Mesh.
8. If unused prosthesis has been in contact with instruments or supplies used on a patient or contaminated with body fluids, discard with care to prevent risk of transmission of viral infections.

## **PRECAUTIONS**

1. Please read all instructions prior to use.
2. Only physicians qualified in the appropriate surgical techniques should use this device. Users should be familiar with strength and mesh size requirements. Improper selection, placement, positioning and fixation of the devices can cause subsequent undesirable results.

## **ADVERSE REACTIONS**

In pre-clinical testing, PHASIX™ Mesh elicited a minimal tissue reaction characteristic of foreign body response to a substance. The tissue reaction resolved as the mesh was resorbed. Possible complications include infection, seroma, pain, mesh migration, wound dehiscence, hemorrhage, adhesions, hematoma, inflammation, extrusion and recurrence of the hernia or soft tissue defect.

## **DIRECTIONS FOR USE**

PHASIX™ Mesh may be cut to shape or size desired for each specific application. To prevent recurrences when repairing hernias, a mesh larger than the defect is required to ensure adequate coverage. The mesh is to be positioned so its edges extend beyond the margins of the defect.

It is recommended that surgical fixation be placed  $\frac{1}{4}$  to  $\frac{1}{2}$  inches (6 to 12mm) apart at a distance approximately  $\frac{1}{4}$  inch (6mm) from the edge of the mesh. The edges are then fixated to assure proper closure under correct tension.

## **HOW SUPPLIED**

PHASIX™ Mesh is available in single packets as a sterile, undyed fabric mesh in single sheet sizes of varying widths and lengths.

## **STORAGE**

Store at room temperature. Avoid prolonged exposure to elevated temperatures. The indicator should be white or light grey. If the indicator is black on the box, check the indicator on the foil pouch. If the indicator is black on the foil pouch, do not use the product.

## **TRACEABILITY**

A traceability label that identifies the type, size, expiration date and lot number of the device is attached to every package. This label should be affixed to the patient's permanent medical record to clearly identify the device that was implanted.

Copyright © 2010 C. R. Bard, Inc. All Rights Reserved.

**Bard, Davol and Phasix** are trademarks and/or registered trademarks of C. R. Bard, Inc. or an affiliate.

### **Appendix 3: Surgical Site Infection Classification**

Superficial Incisional Surgical Site Infections (SSI)

Infection occurs within 30 days after the operation

and

Infection involves only the skin or subcutaneous tissue around the incision and at least one of the following:

1. Purulent drainage with or without laboratory confirmation, from the superficial incision.
2. Organisms isolated from an aseptically obtained culture of fluid or tissue from the superficial incision.
3. At least one of the following signs or symptoms of infection: pain or tenderness, localized swelling, redness or heat and superficial incision is deliberately opened by a surgeon, unless the culture is negative.
4. Diagnosis of superficial incisional SSI by the surgeon or attending physician.

NOTE: Do not report the following as SSI:

1. Stitch abscesses (minimal inflammation and discharge confined to the points of suture penetration)
2. Infection of the episiotomy or neonatal circumcision sites
3. Infected burn wound.
4. Incisional SSI that extends into the fascial and muscle layers (see definition for Deep Incisional Surgical Site Infections below).

Note: Specific criteria are used for identifying infected episiotomy and circumcision sites and burn wounds.

#### **Deep Incisional SSI**

Infection occurs within 30 days after the operation if no implant is left in place or within one year if implant is in place and the infection appears to be related to the operation; and

Infection involves deep soft tissues (e.g., fascia and muscle layers) of the incision and at least one of the following:

1. Purulent drainage from the deep incision but not from the organ/space of the surgical site.
2. A deep incision spontaneously dehisces or is deliberately opened by a surgeon when the patient has at least one of the following signs: fever ( $>38^{\circ}\text{C}$ ), localized pain or tenderness unless the culture is negative.
3. An abscess or other evidence of infection involving the deep incision is found on direct examination, during reoperation, or by histopathologic or radiologic examination.
4. Diagnosis of a deep SSI by a surgeon or attending physician.

Notes:

1. Report infection that involves both superficial and deep incision as deep incisional SSI.
2. Report an organ / space SSI that drains through the incision as deep incisional SSI.

#### **Appendix 4: Surgical Wound Classification**

- Class I/Clean: An uninfected operative wound in which no inflammation is encountered and the respiratory, alimentary, genital, or uninfected urinary tract is not entered. In addition, clean wounds are primarily closed and, if necessary, drained with closed drainage. Operative incisional wounds that follow non-penetrating (blunt) trauma should be included in this category if they meet the criteria.
- Class II/Clean-Contaminated: An operative wound in which the respiratory, alimentary, genital, or urinary tracts are entered under controlled conditions and without unusual contamination. Specifically, operations involving the biliary tract, appendix, vagina, and oropharynx are included in this category, provided no evidence of infection or major break in technique is encountered.
- Class III/Contaminated: Open, fresh, accidental wounds. In addition, operations with major breaks in sterile technique (e.g., open cardiac massage) or gross spillage from the gastrointestinal tract, and incisions in which acute, non-purulent inflammation is encountered including necrotic tissue without evidence of purulent drainage (e.g., dry gangrene) are included in this category.
- Class IV/Dirty-Infected: Old traumatic wounds with retained devitalized tissue and those that involve existing clinical infection or perforated viscera. This definition suggests that the organisms causing postoperative infection were present in the operative field before the operation.

STATISTICAL ANALYSIS PLAN

Title: A Prospective, Multi-Center All Comers Study of a Novel Resorbable Mesh (Phasix™ Mesh) for Ventral or Incisional Hernia Repair

Protocol No.: DVL-HE-015

Study Device: Phasix™ Mesh

Sponsor: Davol Inc.
Subsidiary of C. R. Bard, Inc.
[name]
[name]
[contact]

Prepared By: [name]
C.R. Bard
[name]
[name]

Revised By : [name]
C.R. Bard
[name]
[name]

Version & Date: Version 1.0 February 02, 2017

Table of Contents

1	Introduction.....	3
2	Study Objective and Endpoints.....	3
2.1	Study Objective.....	3
2.2	Study Endpoints	3
2.2.1	Primary Endpoint.....	3
2.2.2	Secondary Endpoints	3
3	Study Design.....	3
3.1	Overview	3
3.2	Sample Size Consideration	4
3.3	Study Procedure	4
4	Analysis Sets.....	4
4.1	By visit interval.....	4
5	Statistical Analysis of the Primary Endpoint	5
6	Statistical Analysis of the Secondary Endpoint.....	6
6.1	Device related adverse event incidence	6
6.2	Quality of life assessments (Carolinas Comfort Scale® and SF-12® - 12-item short form health survey)	6
6.3	Surgical procedure time as measured from incision to closure (skin to skin)	6
6.4	Length of hospital stay post index surgical procedure.....	7
6.5	Number of study-related post-operative surgical procedures and admissions.....	7
6.6	Number of study-related post-operative visits unrelated to standard of care	7
6.7	Incidence of Seroma.....	7
7	Statistical Analyses of Other Endpoints	7
7.1	Subjects Dispositions	7
7.2	Protocol Deviations.....	7
7.3	Demography and Background Disease Characteristics	8
7.4	Prior/concomitant medication.....	8
7.5	Follow-up Period	8
7.6	Intra-operative characteristics	8
7.7	Device failure, malfunctions and defects.....	9
7.8	Safety Endpoints	9
7.8.1	Adverse Event	9
7.8.2	Mesh Infection.....	9
7.8.3	Surgical Site Infection	9
7.8.4	CDC Wound Classification	9
7.8.5	Reoperation.....	9

1 Introduction

This document provides details of the statistical analysis plan (SAP) for the C.R. Bard, Inc. protocol DVL-HE-015 for the final analysis. The statistical methods described here are based on the analyses proposed in the Final Protocol issued on **August 21, 2014, Version 3.0**.

All data processing, summarization, and analyses will be performed using Statistical Analysis System (SAS), Version 9.3 software package.

2 Study Objective and Endpoints

2.1 Study Objective

The objective of this single-arm observational study is to collect additional data on safety, performance, and effectiveness of Phasix™ Mesh in subjects requiring primary ventral or incisional hernia repair.

2.2 Study Endpoints

2.2.1

Primary Endpoint

Hernia Recurrence Rate

Hernia recurrence rates will be assessed by physical examination at each study visit through 24 months. A recurrent hernia will be defined as any hernia identified or confirmed by the investigator, during any study follow-up visit, in approximately the same position as the hernia repaired in the study procedure. Potential hernias identified via incidental magnetic resonance imaging (MRI) or computed tomography (CT) scan will be evaluated by the operating surgeon for clinical significance and confirmation of hernia recurrence.

2.2.2

Secondary Endpoints

1. Device related adverse event incidence
2. Quality of life assessments (Carolinas Comfort Scale® and SF-12® - 12-item short form health survey)
3. Surgical procedure time as measured from incision to closure (skin to skin)
4. Length of hospital stay post index surgical procedure
5. Number of study-related post-operative surgical procedures and admissions
6. Number of study-related post-operative visits unrelated to standard of care.
7. Incidence of Seroma.

3 Study Design

3.1 Overview

This is a prospective, multi-center, single-arm, observational study designed to collect additional data on safety, performance and effectiveness of Phasix™ Mesh for primary ventral or incisional or first-recurrent hernia repair. Follow-up visits will be conducted at 1, 3, 6, 12, 18, and 24 months following surgery. See Section 3.3, Table 1 for a detailed schedule of study visits and procedures.

3.2 Sample Size Consideration

This study is projected to enroll up to 30 subjects at approximately 5 sites. The sample size of 30 subjects is based on potential adequacy of data to meet the study objectives. It is not based on any statistical consideration.

3.3 Study Procedure

An overview of the study visit schedules is shown in Table 1, which summarizes the study procedures to be performed at each study visit.

Table 1: Time and Events Schedule

Study Procedure	Screening and Baseline Period	Surgery	1 Month Visit	3 Month Visit	6 Month Visit	12 Month Visit	18 Month Visit	24 Month Visit	Unscheduled Visit/Early Termination
Visit Window (days)	Within 60 days of consent	0	30 ± 7	90 ± 30	180 ± 30	365 ± 30	545 ± 30	730 ± 30	--
Describe study to potential subject	X								
Obtain informed consent	X								
Verify eligibility criteria	X	X							
Collect demographics and medical history	X								
Conduct physical examination	X		X	X	X	X	X	X	X
Placement Procedure of Device		X ¹							
Carolinas Comfort Scale®	X		X	X	X	X	X	X	X
SF-12®	X		X	X	X	X	X	X	X
Collect adverse events/ complications		X	X	X	X	X	X	X	X
Collect pain medication usage	X					X		X	

¹ See Protocol Section 6.2 for surgical procedure details

4 Analysis Sets

The Intent-to-treat (ITT) population consists of all enrolled subjects who have signed the Informed Consent Form. The modified ITT (mITT) population is defined as those subjects in the ITT population in whom Phasix™ Mesh has been implanted. All analyses will be primarily based on the mITT population.

4.1 By visit interval

There are several tables needed by interval presentation. If the data are collected at each assessment, then the interval will be targeted at each of the visit. If the data are collected by date only on unscheduled CRF, it will be used to separate the intervals. See below table as guidance on how to separate the intervals.

Visit	Visit Window	Interval	
		Term	Days
1 month	Day 30 ± 7 days	Post OP – 1 month	0-37 days
3 month	Day 90 ± 30 days	>1 month – 3 month	38-120 days
6 month	Day 180 ± 30 days	>3 month – 6 month	121-210 days
12 month	Day 365 ± 30 days	>6 month – 12 month	211-395 days
18 month	Day 545 ± 30 days	>12 month – 18 month	396-575 days
24 month	Day 730 ± 30 days	>18 month – 24 month	576 days-end of study/760 days (whichever is earlier)
End of Study (if > 24 month upper window)	NA	>24 months - End of Study	761 days-end of study

5 Statistical Analysis of the Primary Endpoint

There is no formal statistical hypothesis for this observational post-market study. The study will follow eligible patients implanted with the Phasix™ Mesh for hernia repair in order to assess long-term recurrence rates.

The primary endpoint of the study is Hernia Recurrence Rate.

Hernia recurrence will be assessed by physical examination at each study visit through end of study. A recurrent hernia will be defined as any hernia identified or confirmed by the investigator, during any study follow-up visit, in approximately the same position as the hernia repaired in the study procedure. Potential hernias identified via incidental magnetic resonance imaging (MRI) or computed tomography (CT) scan will be evaluated by the operating surgeon for clinical significance and confirmation of hernia recurrence.

The event will be identified if either of the following questions on “HERNIA RECURRENCE” was answered “Yes”:

“Was there any Evidence of Hernia Recurrence in the Same Approximate Location as the Index Procedure Identified by Physical Exam?”

or

“Was there any Evidence of Hernia Recurrence in the Same Approximate Location as the Index Procedure Identified by Any Other Means?”

Only the first hernia recurrence of each subject will be counted in the calculation of the hernia recurrence rate. The hernia recurrence rate will be reported for the whole follow up period (post-op to end of study) and by visit using the intervals defined in section 4.1. Only the subjects who did not discontinue the study before the visit window start will be included in the denominator. The 95% confidence intervals of the rates will be estimated by the Binomial exact method.

Kaplan-Meier survival analysis will be performed to estimate the event rates at various time-points (1 month, 3 month, 6 months, 12 months, 18 month, 24 month, End of Study (if out of 24 month visit upper window)). The time to first event will be the time from index-procedure to the first occurrence of the first event.

6 Statistical Analysis of the Secondary Endpoint

The following secondary endpoints will be summarized using descriptive statistics. The secondary endpoints are described in Section 2.2.2.

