## 6.5 Withdrawal and/or Early Termination

Subjects will be informed that they have the right to withdraw from the study at any time, without affecting their future care. Subjects may also be discontinued from the study, if the Investigator determines it is in the best interest of the subject.

Additionally, subjects may be discontinued for reasons including, but not limited to the following:

- Consent is withdrawn
- Lost to follow-up (LTF)
- Death
- Investigator withdrawal of subject
- Sponsor's decision
- Other

A subject is considered LTF if the investigational site personnel are unable to locate the subject despite two documented attempts to notify the subject via telephone and a third attempt by certified mail.

A subject is considered an Early Termination (ET), if discontinuation occurs after successful implant of the test device. The site should attempt to bring the subject back to complete all ET visit study procedures (see Table of Study Events).

Once a subject discontinues from the study, the Investigator must complete a Study Completion eCRF and the reason for subject discontinuation must be fully documented.

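### SAP section 5 counts by-visit recurrences over the section 4.1 intervals but cuts the denominator at the later visit window start, so the two do not match

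*SAP*

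**What the plan says.** SAP section 5 (primary endpoint) reports the recurrence rate for the whole follow-up period and "by visit using the intervals defined in section 4.1". It counts one event per subject: "Only the first hernia recurrence of each subject will be counted in the calculation of the hernia recurrence rate". The denominator rule is: "Only the subjects who did not discontinue the study before the visit window start will be included in the denominator". Confidence intervals are 95% exact binomial. A Kaplan-Meier analysis, timed from the index procedure, is added.

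The table in SAP section 4.1 has one column for the visit window (target day plus or minus a tolerance) and another for the interval. For the 12-month visit the window is "Day 365 ± 30 days", that is days 335 to 395, while the interval runs from day 211 to day 395. The last row, beyond 24 months, has the interval "761 days-end of study" and NA as its visit window. For off-schedule data section 4.1 says: "If the data are collected by date only on unscheduled CRF, it will be used to separate the intervals".

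Protocol section 6.5 says of a subject who leaves after implantation: "The site should attempt to bring the subject back to complete all ET visit study procedures". The schedule (Protocol section 6.4, SAP Table 1) puts unscheduled and early-termination visits in one column, with a physical examination and no window. Protocol section 6.3.4 applies the unscheduled-visit procedures to any abdominal evaluation during follow-up.

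**The concern.** The numerator and the denominator of one proportion begin on different days. Events count from the start of the interval. Subjects count only if they were still in the study when the visit window opened, which is later in every row. Between those two days lies a gap in which a recurrence can be found and its subject can leave.

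Such a subject supplies an event but is not one of the subjects it is divided by. The numerator is then no longer a subset of the denominator, and the exact binomial method, which assumes x events among n subjects, does not apply. A subject who leaves in the gap without a recurrence is also removed, despite being under observation for part of the interval.

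By-visit rates with 95% confidence intervals are the form in which Protocol section 7.3 says the primary endpoint will be reported, with Kaplan-Meier as an addition. With at most 30 subjects, the placing of a single subject shows in the table.

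**Working it through.** **Inputs.** Target days, tolerances and intervals come from SAP section 4.1; the numerator and denominator rules come from SAP section 5.

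**Step 1: reproduce the plan's intervals.** Interval start = upper limit of the previous window + 1 (day 0 for the first). Interval end = target + tolerance. For 12 months: start 180 + 30 + 1 = 211, end 365 + 30 = 395. All six stated intervals reproduce exactly.

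**Step 2: find the gaps.** Window start = target − tolerance. Gap = window start − interval start.

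| Visit | Interval (days) | Window (days) | Gap (days) | Gap length / interval length |
|---|---|---|---|---|
| 1 month | 0–37 | 23–37 | 0–22 | 23/38 (61%) |
| 3 month | 38–120 | 60–120 | 38–59 | 22/83 (27%) |
| 6 month | 121–210 | 150–210 | 121–149 | 29/90 (32%) |
| 12 month | 211–395 | 335–395 | 211–334 | 124/185 (67%) |
| 18 month | 396–575 | 515–575 | 396–514 | 119/180 (66%) |
| 24 month | 576–760 | 700–760 | 576–699 | 124/185 (67%) |
| Beyond 24 months | from 761 | NA | undefined | – |

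The gaps sum to 23 + 22 + 29 + 124 + 119 + 124 = 441 of 761 days (58%). That is a share of calendar days, not of events or subjects.

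**Step 3: follow one subject.** A recurrence is found at an early-termination examination on day 300 and the subject leaves that day. Since 211 ≤ 300 ≤ 395, the event belongs to the 12-month interval. Since 300 < 335, the subject discontinued before the window opened and is outside the denominator.

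**Step 4: size, on assumed counts.** The documents give no dropout or recurrence rate, so these counts are illustrations only. Suppose 28 subjects are in the study at day 211. Two leave on days 211–334, one of them with a recurrence, and one retained subject recurs in the interval.

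- As worded: 2 events over 28 − 2 = 26, or 7.7% (nominal exact 95% CI 0.9 to 25.1), with one of the two events from outside the 26.
- Matched to the interval: 2/28 = 7.1% (0.9 to 23.5).
- Difference: 7.69 − 7.14 = 0.55 percentage points.

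Other assumed cases, each with 30 subjects at the interval start:

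| Assumed case | As worded | Matched |
|---|---|---|
| One recurrence, in the only gap exit | 1/29 = 3.4% | 1/30 = 3.3% |
| Three recurrences, one of them in the only gap exit | 3/29 = 10.3% | 3/30 = 10.0% |
| Three recurrences and three gap exits, one exit with a recurrence | 3/27 = 11.1% | 3/30 = 10.0% |

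The shift is upward and at most about one percentage point in these cases.

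**The case against.** The strongest reply is that *visit window start* is loose wording for the interval start. The denominator sentence directly follows the reference to the section 4.1 intervals, and section 4.1 calls its table guidance. On that reading the mismatch disappears. It may be what was meant, but it is not what is written: the section 4.1 table and both schedules use the term visit window for target plus or minus tolerance, and section 4.1 gives the interval its own column. If it was meant, the fix only records it.

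A second reply is that section 4.1 places by date only the data collected by date on the unscheduled form, and does not say that early-termination findings use that form. This stands as a gap in the text. Placing them by date is still a reasonable inference, because the schedules put unscheduled and early-termination visits in one column without a window.

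A third reply is that the case is rare and the study descriptive. It needs a recurrence and an exit in the same gap. The discontinuation reasons in Protocol section 6.5 do not name recurrence (the list is not exhaustive), and no dropout rate is given. There is no hypothesis to test, and the whole-period rate and Kaplan-Meier estimates keep the event. All of this stands, and it limits the importance of the point. It does not make the rule coherent.

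**Conclusion.** The point holds for the by-visit recurrence rates only. As worded, SAP section 5 can give a rate whose numerator is not contained in its denominator, and it removes event-free subjects who leave in the gap. For the row beyond 24 months it defines no denominator at all. The numerical effect is likely small (7.7% against 7.1% in the main illustration, on assumed counts), and its frequency cannot be estimated from the documents. The conclusion rests on reading visit window as the section 4.1 column of that name and on placing off-schedule findings by date.

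Three stronger readings are not supported:

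- A reader might infer that the recurrence would be dropped and the rate biased downward. SAP section 5 has no rule that removes an event from the numerator; it says each subject's first recurrence is counted.
- A reader might infer that the primary endpoint as a whole is compromised. The whole-period rate has no later window start, and the Kaplan-Meier analysis runs from the index procedure, so both keep the event.
- A reader might take the 58% as the share of events at risk. It counts days, and the documents do not link exit to recurrence.

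**What to change.** In SAP section 5, replace the visit window start in the denominator rule with the start of the section 4.1 interval: day 0, 38, 121, 211, 396 or 576, and day 761 for the row beyond 24 months. Add that any subject whose first recurrence is dated in an interval is always in that interval's denominator. The first change reduces the gap to zero in all six rows that have a visit window and gives the last row a denominator. The second keeps the numerator within the denominator however an exit visit is dated.

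Do not add a condition that the subject was assessed in the interval. Missed assessments are a separate question, and in the main illustration that condition would give 2/27 if the event-free leaver had no examination.

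The cost is a short wording change in the SAP and a matching programming change. No new data are needed.
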